#### 4.1.3 Pharmacokinetic Analysis Set

The PK Analysis set is defined as all participants who receive STAR-0215 and have at least 1 concentration post-dose sample available to enable assessment of PK. Additionally, this analysis set will have no important protocol deviations that could affect the evaluation of PK parameters.

#### 4.1.4 Pharmacodynamic Analysis Set

The PD Analysis set is defined as all participants who received at least 1 dose of STAR-0215 and had PD assessments at baseline and at least 1 post-baseline visit assessment. Additionally, this analysis set will have no important protocol deviations that could affect the evaluation of PD parameters.

### 4.2 Protocol Deviations

Protocol Deviations will be classified as Important or Non-Important. Important Protocol Deviations may lead to removal of participants' data from efficacy, PK or PD analysis. The list of protocol deviations will be reviewed by the Sponsor, the principal investigator and the study statistician. Determination of whether important deviations have an impact on any of efficacy,

PK or PD assessments, will be determined prior to any formal analysis. A report of Protocol Deviations (excel or csv format) will include important /non-important distinctions, category, description, population impact (each of efficacy, PK or PD), in addition to dates and other relevant variables.

The number (%) of participants with at least one protocol deviation and the number (%) of participants with at least one important protocol deviation will be summarized. For the important protocol deviations, the number (%) of participants in each deviation category will be presented.

## 5 DATA HANDLING

### 5.1 Computing Environment

All descriptive statistical analyses will be performed using SAS statistical software (Version 9.4), unless otherwise noted. Medical History and adverse events will be coded using Medical Dictionary for Regulatory Activities (MedDRA) 25.1 or later. Concomitant medications will be coded using World Health Organization (WHO) Drug version Sept 2022 or later.

### 5.2 Data Conventions

- **Period definition:**
  - **Screening/Run-In Period:** Starts at the Screening visit until the day before first treatment, approximately Study Day -56 to -1. If a participant has an HAE attack during the Run-In period before Day 1, all signs and symptoms of the HAE attack must be resolved before dosing.
  - **Treatment & Follow-up Period:** The period from date of first dose to End of Study Date.
  - **End of Study Date:** The latest of date of Early Termination visit or as designated by “End of Study” CRF page.
  - **Treatment Period (for HAE assessments)** is defined in [Section 9.1](#); for this period the last scheduled visit for each cohort is Day 168 visit for cohort 1, Day 251 visit for cohort 2, and Day 195 visit for cohort 3. The last assessment date or last dose date can be used for participants that have not reached the end of their cohort’s treatment period.
  - **First Dose Period (for HAE assessments)** is defined as the first dose until participant’s second dose (cohorts 2 & 3) or end of treatment period.
  - **Study day:** Relative to the date of first treatment of STAR-0215: assessment date – first treatment date (+1 if assessment is after first treatment).
- **Conversion factors:**
  - 1 month = 30.4375 days
  - 1 year = 365.25 days
  - 1 week = 7 days
- **Additional rules**
  - (Absolute) Change from baseline = Value at the time point – Baseline value.
  - Relative change from baseline = [(Value at the time point – Baseline value) / Baseline value] x 100.

- % inhibition (of pharmacodynamic assessments) =  $1 - [\text{postdose rate} / \text{predose rate}] \times 100$ .
- Duration on Study = (End of Study Date – Date of First STAR-0215 treatment) +1.
- Duration of Treatment Period = (Last Treatment period assessment date – Date of First STAR-0215 treatment) +1.

### 5.3 Methods of Pooling Data

Not applicable.

### 5.4 Withdrawals, Dropouts, Loss to Follow-up

For participants who withdraw from the study prior to their completion for any reason, all data compiled up to the point of discontinuation will be used for analysis.

### 5.5 Visit Windows

Visit Windowing will not be applied. Summary tables or graphs will display scheduled visits and time points only; Unscheduled visits results will be listed, but not included in tables or graphs.

## 6 STATISTICAL METHODS

### 6.1 Sample Size Justification

This is the first time STAR-0215 is being used in participants with HAE. No formal sample size calculations have been performed.

Up to 28 participants will be dosed in this study. This is considered adequate to characterize the safety, tolerability, clinical activity, PK, PD, and immunogenicity of STAR-0215.

No placebo group will be used in this study; each participant will serve as their own control. Data collected during the Run-In period will be used to establish each participant's baseline.

### 6.2 General Statistical Methods

#### 6.2.1 General Methods

All outputs will be incorporated into Microsoft Excel or Word files, sorted and labeled according to the International Conference on Harmonization (ICH) recommendations, and formatted to the appropriate page size(s).

Tabulations will be produced for appropriate demographic, baseline, efficacy, PK, PD, Immunogenicity and safety parameters. For categorical variables, summary tabulations of the number and percentage within each category (with a category for missing data) of the parameter will be presented. For continuous variables, the mean, median, standard deviation, Q1, Q3, minimum and maximum values will be presented. The PK summaries will additionally include the percent coefficient of variation (CV%), geometric mean, and geometric CV%. Descriptive statistics for categorical variables will consist of frequency counts and percentages.

Results will be presented by cohort.

No formal statistical hypothesis testing will be performed. Summary statistics will be presented, as well as 95% confidence intervals (CI) on selected parameters, as described in the sections below.

#### 6.2.2 Definition of Baseline

For the analysis of HAE attacks, the Run-In Period will be considered as Baseline for rate, incidence or duration of HAE attacks.

For all other endpoints baseline is defined as the last non-missing assessment prior to the first dose of STAR-0215.

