4. INVESTIGATIONAL PLAN

4.1. Overall Study Design

STAR-0215-201 is a Phase 1b/2, multicenter, single and multiple dose study to assess the safety, tolerability, efficacy, PK, PD, and immunogenicity of STAR-0215 in participants with Type I or Type II HAE.

Properly consented participants will undergo screening assessments according to the inclusion and exclusion criteria ([Section 5.1](#) and [Section 5.2](#), respectively) and immediately enter the Run-In period. During the Run-In period, HAE attack information will be collected to determine if a participant meets the eligibility requirement of experiencing at least 2 HAE attacks during this time period and to establish a baseline prior to STAR-0215 administration. If a participant has an HAE attack during the Run-In period before Day 1 (first dose of STAR-0215), all signs and symptoms of the HAE attack must be resolved before dosing. A washout period for on-demand treatment is not required. The Run-In period may be extended after consultation with the Medical Monitor. In Cohorts 2 and 3, if a participant has an HAE attack immediately before the second dose (Day 84 and Day 28, respectively), signs and symptoms of the HAE attack should be improving per participant report prior to STAR-0215 administration; a washout period for on-demand treatment is not required before the second dose is administered.

In Cohort 1, each participant who has completed the Run-In period and is eligible for STAR-0215 administration will receive 1 dose of STAR-0215 on Day 1. When Cohort 1 has completed dosing, the SRC will review the cohort's cumulative safety data from the Screening/Run-In period through 21 days after dosing. Progression to Cohort 2 dosing will occur if there are no concerning safety signals. Details of the SRC's review are provided in [Section 4.2](#).

In Cohort 2, each eligible participant will receive 2 doses of STAR-0215, the first on Day 1 and the second on Day 84. When 6 participants in Cohort 2 have received Dose 1, progression to dosing of Cohort 3 will begin.

In Cohort 3, each eligible participant will receive 2 doses of STAR-0215, the first on Day 1 and the second on Day 28.

Provided no safety concerns are noted from a cumulative review of safety data from this study and the ongoing FIH study (STAR0215-101), [REDACTED] and [REDACTED] may be explored in [REDACTED] would be added through an amendment to the protocol.

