4.5. Duration of Treatment and Duration of Study

Individual participants will receive 1 dose of STAR-0215 (Cohort 1; Day 1) or 2 doses (Cohort 2; Days 1 and 84, and Cohort 3; Days 1 and 28). The duration of study participation for each participant, including the Screening and Run-In period, is up to [REDACTED], or [REDACTED] days in Cohorts 1, 2, and 3, respectively. The study is composed of 3 periods, as follows:

- Screening/Run-In: at least 56 days
- Treatment Period: Individual participants will receive STAR-0215 on Day 1 (Cohort 1), Day 1 and 84 (Cohort 2), or Day 1 and 28 (Cohort 3).
- Follow-up Period: approximately 6 months after the last dose of STAR-0215 (Day 168 for Cohort 1, Day 251 for Cohort 2, and Day 195 for Cohort 3). At this time, participants who are willing and eligible to consent can begin participation in the long-term open label extension study (STAR-0215-202).
- Follow-up Period: For participants who do not participate in the long-term open label extension study, monitoring will be performed through [REDACTED] months after the last dose of STAR-0215 in all cohorts (Day [REDACTED] in Cohort 1, Day [REDACTED] in Cohort 2, and Day [REDACTED] in Cohort 3) through regular contacts and scheduled study visit.

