8. Agree not to donate or store eggs or undergo assisted reproductive or fertility treatment during the study and for a total of ■ months after the last dose of STAR-0215.

9. Experienced at least 2 HAE attacks during the Run-In period, as confirmed by an investigator based on meeting the protocol-specified definition of an HAE attack ([Section 7.12](#)).

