7.2. Screening/Eligibility

All screening evaluations must be completed and documented by the Investigator within the specified Screening and Run-In period (refer to the SOAs in [Section 1.1](#)). The Investigator will confirm the participant's eligibility before STAR-0215 administration on Day 1.

Screen failures are defined as participants who provide informed consent to participate in the clinical study but who do not meet the eligibility criteria for participation in this study. Individuals who do not meet the criteria for participation in this study may be rescreened once, provided the reason for screen failure is considered transient and likely to change before rescreening and after consultation with the Medical Monitor. If a participant is rescreened within 28 days of the date of screen failure, the following screening assessments do not need to be repeated unless they were the cause of the screen failure: chemistry, hematology, and virus serology laboratory evaluations. Screening laboratory evaluations may be repeated at the discretion of the Investigator.

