7.3. Diagnosis and History of Hereditary Angioedema

Diagnosis of HAE will be based on clinical history, age of onset of first angioedema symptoms, and blood tests of C1-INH antigen or functional level and C4 level. Testing for C1-INH and C4 will be performed according to the central laboratory's standard procedure.

Date of diagnosis, onset of symptoms, and type of HAE (I or II) will be collected. Historical HAE attack information, which includes the number of HAE attacks in the 12 months prior to Screening, will be collected at Screening.

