7.12. Hereditary Angioedema Attack Information

Hereditary angioedema attacks will be assessed throughout the study to evaluate the efficacy of STAR-0215. The HAE attack information collected during the Run-In period will be used to establish a participant's eligibility and baseline. Study staff will collect HAE attack information from participants weekly through 6 months following the last dose administered. Investigators will assess this collected information against the HAE attack definition ([Section 7.12.1](#)) to confirm occurrence of HAE attacks. The clinical information related to any HAE attacks that will be collected will include, but not be limited to, attack location, severity, time of onset, duration of attack, hospitalization status, and treatment with any acute on-demand therapy.

If a participant experiences HAE attacks during the study, they will be permitted standard-of-care on-demand treatment as prescribed by their physician ([Section 6.3.2](#)).

If a participant has an HAE attack before Day 1 (first dose of STAR-0215), all signs and symptoms of the HAE attack must be resolved before dosing. A washout period for on-demand treatment is not required. In Cohorts 2 and 3, if a participant has an HAE attack immediately before the second dose (Day 84 and Day 28, respectively), signs and symptoms of the HAE attack should be improving per participant report prior to STAR-0215 administration; a washout period for on-demand treatment is not required before the second dose is administered.

Guidance on the collection of HAE attack information with respect to AE collection is provided in [Section 8.2.1](#).

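### The run-in count that qualifies participants is also their only baseline, so mean absolute change in attack rate is expected to be negative even with no drug effect

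*SAP*

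**What the plan says.** SAP 6.2.2 sets the baseline for the attack endpoints: "For the analysis of HAE attacks, the Run-In Period will be considered as Baseline for rate, incidence or duration of HAE attacks". Protocol 7.12 gives the same data two jobs: "The HAE attack information collected during the Run-In period will be used to establish a participant's eligibility and baseline". The eligibility job is in Protocol 5.1, criterion 9: "Experienced at least 2 HAE attacks during the Run-In period, as confirmed by an investigator".

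Protocol 4.5 gives the length as "Screening/Run-In: at least 56 days", and Protocol 4.1 adds that "The Run-In period may be extended after consultation with the Medical Monitor". SAP 5.2 defines the Screening/Run-In period thus: "Starts at the Screening visit until the day before first treatment, approximately Study Day -56 to -1". Protocol 7.2 says that a participant who fails screening "may be rescreened once, provided the reason for screen failure is considered transient and likely to change before rescreening".

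SAP 6.4.1 plans absolute and percentage change from this baseline with 95% CIs, and the proportions of participants with reductions of at least 50%, 70% and 90%. SAP 6.1 confirms that there is no placebo group and that participants are their own controls. SAP 6.2.3 plans no covariate assessment. Neither document mentions regression to the mean or a second baseline.

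Protocol 7.3 records that "the number of HAE attacks in the 12 months prior to Screening, will be collected at Screening". SAP 6.3.2 uses that count only as a baseline characteristic.

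**The concern.** A participant enters only if the run-in count reaches 2. Someone whose true rate is near the threshold gets in when the count is by chance high and stays out when it is low. Among those dosed, the run-in rate therefore overstates the true rate on average, and later counts fall back towards it whatever the drug does. A concurrent control group would show the same fall and so cancel it. Here nothing does.

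At stake are the change from baseline in monthly attack rate, which is the first secondary efficacy endpoint, and the responder proportions derived from it. Under Protocol 9.12, interim efficacy results may inform whether Cohorts 2 and 3 grow to 12 participants each, so the estimates feed decisions as well as the final report.

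**Working it through.** The documents give no bias, power or sample-size figure to reproduce.

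**Inputs from the documents.** Threshold of 2 attacks (Protocol 5.1); run-in of 56 days (Protocol 4.5); 30.4375 days per month (SAP 5.2); attack follow-up of 168, 251 and 195 days for Cohorts 1, 2 and 3 (SAP 5.2). The lowest possible baseline over 56 days is 2/56 × 30.4375 = 1.09 per month.

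**Assumptions, not in the documents.** Attacks are Poisson; the true rate r is the same before and after dosing (no drug effect); r runs from 1 to 3 per month.

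**Formulas.** With X the run-in count and μ = r × 56/30.4375:
- E[X | X ≥ 2] = μ(1 − e^−μ) / (1 − e^−μ − μe^−μ)
- expected baseline B = E[X | X ≥ 2] × 30.4375/56
- null absolute change = r − B; null change in ratio of means = r/B − 1
- null mean percent change = μ × E[1/X | X ≥ 2] − 1

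**Worked at r = 1.** μ = 1.840 and e^−μ = 0.1589, so E[X | X ≥ 2] = 1.5476/0.5489 = 2.82 and B = 1.53. The change is 1 − 1.53 = −0.53, and 1/1.53 − 1 = −35%. E[1/X | X ≥ 2] = 0.393, so mean percent change is 1.840 × 0.393 − 1 = −28%.

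| True rate per month | Expected baseline | Absolute change | Ratio of means | Mean percent change |
|---|---|---|---|---|
| 1 | 1.53 | −0.53 | −35% | −28% |
| 1.5 | 1.84 | −0.34 | −19% | −6% |
| 2 | 2.21 | −0.21 | −10% | +7% |
| 3 | 3.07 | −0.07 | −2% | +17% |

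The last column changes sign because the noisy baseline is also the divisor.

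**Spread between participants.** With gamma-distributed true rates (shape 2, CV about 0.7), the ratio of means falls by 24% at a population mean of 1 per month (1.83 to 1.40, change −0.43) and by 9% at 2 per month (change −0.24).

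**Responders with no drug effect.** At 1 per month, 36%, 31% and 27% of participants show at least a 50% reduction over 168, 195 and 251 days. Over 168 days, 10% reach 70% and about 1% reach 90%. At 2 per month, 13% reach 50% over 168 days.

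**Confidence interval.** The chance that the 95% t-interval for mean absolute change lies wholly below zero with no drug effect (nominally 2.5%), for cohorts of 4, 6 and 12:
- single rate of 1 per month: 16%, 31%, 70%
- gamma mean 1 per month, shape 2: 12%, 18%, 34%
- single rate of 2 per month: 3%, 4%, 7%

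**Extension and rescreening.** A 28-day extension, with dosing once the second attack occurs and all days in the denominator, shrinks the shift from −0.53 to −0.36 (single rate of 1 per month) or from −0.43 to −0.32 (gamma mean 1, shape 2). Rescreening everyone who fails on count leaves −0.53 unchanged, and moves −0.43 to −0.47 in the mixture.

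**Check on cause.** Replacing the baseline with an equal-length period not used for selection (gamma mean 1, shape 2) gives 1.398 before and 1.398 after. The shift comes from the selection.

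**The case against.** This is an uncontrolled Phase 1b/2 safety study. Efficacy is secondary, SAP 6.2.1 disclaims formal hypothesis testing, and the true rates above are assumed. That is fair context, and at 3 per month or more the shift is minor. It does not remove the point, because estimates and intervals are still reported and may guide cohort expansion.

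Several stronger readings are tempting, and the documents do not support them:
- *Every change measure favours the drug.* Mean percent change does so only at low rates, and at about 2 per month or more it moves against the drug.
- *Extending the run-in makes it worse.* SAP 5.2 runs the period to the day before first treatment and SAP 6.4.1 divides by its duration, so the added days dilute the shift.
- *Rescreening inflates it.* Only one rescreen is allowed, for a transient reason. A low attack count is neither named nor excluded, and the computed effect is small.
- *All responder thresholds are equally affected.* At a mean true rate of 1 per month or more, only about 1% to 2% would reach a 90% reduction by chance. SAP 6.4.1 plans no CI for the responder proportions, so the point about intervals concerns absolute change.
- *All efficacy results are compromised.* Attack-free proportion and time to first attack do not use the baseline count in their calculation.

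**Conclusion.** The point holds for mean absolute change and the ratio of mean rates, and in part for the 50% and 70% responder proportions. Under the Poisson assumption, a 56-day run-in and no drug effect, the expected change is −0.53 to −0.07 per month for true rates of 1 to 3 per month. The 95% CI for absolute change is shifted by the same amount, and a larger cohort makes an interval that wrongly excludes zero more likely.

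The direction of the shift in absolute change follows from the design. Its size depends on true rates that the documents do not give. A reader might infer that a large observed reduction would be an artefact; these figures do not support that, since the mechanism produces almost no near-complete reductions. It matters most for a moderate effect in participants with about 1 attack per month.

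**What to change.** In SAP 6.4.1, add one prespecified sensitivity analysis, shown beside the main one: absolute change, ratio of mean rates, and 50%, 70% and 90% responder proportions against the 12-month historical attack rate collected under Protocol 7.3. State as a limitation that the run-in baseline is subject to selection at 2 or more attacks. Report how many participants had an extended run-in or were rescreened.

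A count model with the run-in truncated at 2 or more is optional, and only pooled over cohorts. By cohort it is too unstable: at 1 per month the estimated baseline from a truncated Poisson has a 95% sampling range of 0 to 1.95 with 4 participants and 0.25 to 1.71 with 6.

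The cost is SAP wording and modest programming, with no new data or visits. The history is recalled, is not tied to the investigator-confirmed attack definition, and may include time on prophylaxis. It can err in either direction, so it belongs beside the run-in baseline and does not replace it. The reported reduction may be smaller.

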2.1. Background

2.1.1. Hereditary Angioedema

Hereditary angioedema (HAE) is a rare autosomal dominant genetic disease characterized by severe, recurrent, unpredictable, often painful, and sometimes life-threatening swelling in the face, limbs, abdomen, and airway ([Zuraw 2008](#)).

The majority of HAE cases (Type I and Type II) are caused by mutations in the SERPING1 gene that lead to a reduction in the amount (Type I, approximately 85% of patients) or function (Type II, approximately 15% of patients) of C1-esterase inhibitor protein (C1-INH) encoded by this gene ([Zuraw 2008](#); [Busse 2021](#)). The process by which a deficiency in the amount or function of C1-INH leads to HAE is shown in [Figure 1](#). Fully functional C1-INH inhibits the activity of 2 key enzymes in the contact activation system, Factor XIIa and plasma kallikrein: a deficiency in the amount or function of C1-INH results in the unregulated activity of these enzymes ([Craig 2012](#)). The uninhibited activity of the contact pathway in Type I and Type II HAE leads to an unchecked and widespread surge in the production of bradykinin by plasma kallikrein, resulting in excessive and pathologic edema and pain ([Zeerleder 2016](#)).

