2.1.2. Current Treatment Options for Hereditary Angioedema and Unmet Need

Current therapies can be divided into 2 general groupings: (1) historical and not mechanism based (these include attenuated androgens and antifibrinolytics) and (2) mechanism based (purified plasma derived C1-INH, plasma kallikrein inhibitor, and bradykinin B2-R blocker).

Currently, approved HAE drugs are indicated either for prophylaxis or for on-demand treatment of HAE attacks.

Depending on the geographical location, the following drugs may be available for prophylactic use in patients with HAE: substituted androgen danazol, plasma derived C1-INH products (Cinryze®, Haegarda®/SC Berinert®), plasma kallikrein monoclonal antibody (mAb) inhibitor (Takhzyro® [lanadelumab]), and plasma kallikrein small molecule inhibitor (Orladeyo® [berotralstat]).

Similarly, depending on the geographical location, the following drugs may be available for on-demand use in patients with HAE: plasma derived C1-INH (Berinert®), recombinant protein plasma kallikrein inhibitor (Kalbitor® [ecallantide]), bradykinin receptor antagonist (Firazyr® [icatibant]), and recombinant human C1-INH product (Ruconest®).

Despite the existence of approved therapies, many patients still face a major challenge to achieve a satisfactory treatment strategy to prevent HAE attacks. This is primarily due to patients' variable response to approved medications, which leads to unpredictable and incomplete attack prevention, and that dosing and administration regimens require burdensome and often frequent

procedures. Both patients and physicians report a need for less burdensome, easier to administer treatments (Bouillet 2022).

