6.3.2. Permitted Medications

All medications not specified in [Section 6.3.1](#) are permitted at the discretion of the Investigator. Vaccinations, including COVID-19 vaccines, are allowed per local guidelines and regulations; there is a timing restriction for vaccine doses with respect to STAR-0215 administration ([Section 6.3.1](#)), which is also specified in the inclusion criteria ([Section 5.1](#)).

If a participant experiences HAE attacks during the study, they will be permitted standard-of-care on-demand treatment as prescribed by their physician. The date and time of on-demand attack treatment as well as the name and dosage regimen of the treatment must be recorded.

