## 6.5.2 Pharmacodynamics Evaluations

Pharmacodynamic analyses will be conducted on data from participants in the PD Analysis Set. Descriptive statistics will be presented for plasma kallikrein activity levels (as measured by %cHMWK), absolute change and percentage change from baseline levels will be analyzed at each visit. A test comparing the percent change and absolute change from baseline within each group will be calculated and a within group p-value will be presented at each visit and timepoint.

Mean and median activity levels versus time, change from baseline, and percent change from baseline profiles will be plotted by treatment on a linear scale. Individual levels versus time plots by cohort and spaghetti plots with subject level versus time profiles by cohort will also be provided on a linear scale.

Exploratory analyses to assess orthogonal measures of plasma kallikrein enzyme activity (peptide reporter substrate assay) will be performed. Descriptive statistics will be presented for the rate of activity and % inhibition result. A test comparing the % inhibition change and change from baseline to zero within each group will be calculated and a within group p-value will be presented at each visit and timepoint.

The mean and median % inhibition versus time profiles will be plotted by cohort on a linear scale. Individual values versus time plots by treatment and spaghetti plots with subject levels versus time profiles by cohort will also be provided on a linear scale.

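### On-demand C1-INH or a kallikrein inhibitor may be taken shortly before scheduled PD samples, including baseline, and the SAP has no rule for it, so the PD change can mix rescue carry-over with the STAR-0215 effect

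*SAP*

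**What the plan says.** Change in plasma kallikrein activity is a secondary endpoint (Protocol 3), and Protocol 7.13.2 gives the purpose of the PD samples as evaluating the inhibition caused by STAR-0215. PD blood is scheduled at Screening, Day 1 pre-dose and later visits in every cohort.

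**On-demand drugs.** Protocol 2.1.2 lists plasma-derived C1-INH, recombinant C1-INH, a plasma kallikrein inhibitor (ecallantide) and a bradykinin receptor antagonist (icatibant), with availability depending on geography. Protocol 2.1.1 states: "Fully functional C1-INH inhibits the activity of 2 key enzymes in the contact activation system, Factor XIIa and plasma kallikrein".

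**Use and washout.** Protocol 6.3.2 permits on-demand treatment for attacks during the study and requires a record: "The date and time of on-demand attack treatment as well as the name and dosage regimen of the treatment must be recorded". Before Day 1, "all signs and symptoms of the HAE attack must be resolved before dosing" (Protocol 4.1), but "A washout period for on-demand treatment is not required" (Protocol 7.12). For Cohorts 2 and 3, "a washout period for on-demand treatment is not required before the second dose is administered" (Protocol 4.1). For other PD visits there is no rule either way.

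**Analysis.** Baseline is as in SAP 6.2.2: "For all other endpoints baseline is defined as the last non-missing assessment prior to the first dose of STAR-0215". SAP 6.5.2 presents %cHMWK levels and absolute and percentage change from baseline at each visit, with within-group p-values. A second assay is reported as % inhibition, which SAP 5.2 bases on the ratio of post-dose to pre-dose rate. Data are analysed as observed (SAP 6.2.6), without covariates (SAP 6.2.3). Unscheduled results are listed but kept out of tables and graphs (SAP 5.5).

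**The concern.** Three of the four listed on-demand options act on the quantity that the PD endpoint measures. Permitted use is not a protocol deviation, so the PD Analysis Set does not remove affected participants. On-demand use is summarised in SAP 6.4.4 and 6.6.5 but is never linked to the PD values.

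The bias has no single direction. A rescue-suppressed Day 1 value makes later inhibition look too small at every visit for that participant, while a rescue-suppressed post-dose value makes inhibition look too large at that visit. With 4 to 12 participants per cohort, one person can shift a mean. At stake is whether the reported PD change can be attributed to STAR-0215 alone.

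There is also a smaller gap. The baseline rule does not say whether an unscheduled run-in sample, drawn at an attack visit, could become baseline if the Day 1 value is missing. SAP 5.5 bars such results from tables and graphs but does not address their use in deriving baseline.

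**Working it through.** The plan gives no PD effect size and no formal sample size calculation (SAP 6.1), so there is no planned figure to reproduce. The calculations below are illustrations.

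**1. How often a Day 1 baseline could be affected**

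Inputs from the documents: at least 2 attacks in the run-in (Protocol 5.1, criterion 9), run-in of at least 56 days (Protocol 4.5), and 30.4375 days per month (SAP 5.2). Assumptions: attacks follow a Poisson process, every attack is treated with a kallikrein-active drug, and carry-over lasts w = 1 to 7 days.

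Minimum rate, if the run-in is exactly 56 days: 2/56 × 30.4375 = 1.09 per month.

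P(onset in the w days before the sample) = 1 − exp(−rate × w / 30.4375).

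P(at least one of n) = 1 − (1 − P)^n.

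| w (days) | per participant | n = 4 | n = 6 | n = 12 |
|---|---|---|---|---|
| 1 | 3.5% | 13% | 19% | 35% |
| 3 | 10.2% | 35% | 47% | 72% |
| 7 | 22.1% | 63% | 78% | 95% |

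For example, w = 7: 1 − exp(−2/56 × 7) = 1 − exp(−0.25) = 22.1%; for n = 6, 1 − 0.779^6 = 78%.

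At 3 attacks per month the per-participant figures are 9.4%, 25.6% and 49.8%. If only half of attacks are treated with a kallikrein-active drug, at the minimum rate and w = 7, the figure is 1 − exp(−0.125) = 11.8% per participant and 1 − 0.882^6 = 53% for n = 6.

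For a given rate and window these are upper bounds. They count attacks that have not yet resolved, when Day 1 dosing could not proceed, and (apart from the halved case) they treat every attack as rescued with a kallikrein-active drug.

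**2. What one affected value does**

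Let I be true inhibition, and let r_base and r_post be the fractions by which rescue lowers measured activity at baseline and after dosing. These are assumed and taken as multiplicative.

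Reported inhibition = 1 − (1 − I)(1 − r_post)/(1 − r_base).

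With I = 70%:

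| suppression | baseline affected | post-dose affected |
|---|---|---|
| 20% | 1 − 0.30/0.80 = 62.5% | 1 − 0.30 × 0.80 = 76% |
| 30% | 1 − 0.30/0.70 = 57.1% | 1 − 0.30 × 0.70 = 79% |
| 50% | 1 − 0.30/0.50 = 40.0% | 1 − 0.30 × 0.50 = 85% |

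**3. Effect on a cohort mean, true value 70%, one affected baseline**

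- 30% suppression, n = 6: (5 × 70 + 57.1)/6 = 67.9%. For n = 4 it is 66.8%, and for n = 12 it is 68.9%.
- 50% suppression: n = 4 gives (3 × 70 + 40)/4 = 62.5%, n = 6 gives 65.0%, and n = 12 gives 67.5%.

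One affected post-dose value at 30% suppression with n = 6 moves that visit's mean up to (5 × 70 + 79)/6 = 71.5%.

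**The case against.** The strongest reply is that the causal link is assumed. Neither document says how far, or for how long, an on-demand dose shifts the study assays. Attacks must have resolved before Day 1, and the attack-duration categories extend beyond 48 hours, so the short-window rates above are the most inflated. A bradykinin receptor antagonist would not contribute. The SAP also offers protection: activity levels that do not depend on baseline, medians and quartiles, individual and spaghetti plots, and by-subject listings of attacks and HAE medications. In cohorts this small, an odd profile can be traced. The endpoint is secondary and largely descriptive.

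Most of this stands and limits the size of the point. It does not remove it. Resolved symptoms do not mean that the drug has cleared, and listings allow tracing after the fact but give no pre-specified rescue-free estimate.

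It might also be said that Protocol 6.3.1 prohibits kallikrein inhibitors. They appear there within the item on long-term prophylaxis, and Protocol 6.3.2 expressly permits on-demand treatment, so the on-demand route remains open.

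A further objection succeeds. Removing post-rescue values from the main tables could itself bias them. Post-dose rescue follows breakthrough attacks, so the removed values may come from participants whose protection is weakest. The as-observed analysis should therefore stay the main one.

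**Conclusion.** The gap is real and modest. Kallikrein-active rescue may precede any scheduled PD sample, no washout is required before either dose, and the SAP neither flags nor examines the affected values. In those participants, the PD change can mix two drug effects. The illustrated shift in a cohort mean from one affected baseline runs from about 1 percentage point (n = 12, 30% suppression) to 7.5 points (n = 4, 50% suppression), for an assumed true inhibition of 70%. The suppression, the window and the attack process are assumptions, so the actual size cannot be established from the documents.

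Three stronger readings are tempting and not supported:

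- A reader might infer that the PD endpoint is contaminated. The documents show only that it can be, in participants who took these drugs close to a sample.
- A reader might infer that a known share of Day 1 baselines will be affected. The rates above are upper bounds under assumptions.
- A reader might infer that rescue will hide waning and so undermine a 6-month duration claim. Protocol 2.4.1 gives a modelled estimate that concentrations may fall to non-suppressive levels at about 6 months; it does not rest on these PD tables.

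**What to change.** In SAP 6.2.2 and 6.5.2:

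1. Keep the as-observed PD analysis as the main one.
2. Flag every scheduled PD value, including baseline, taken within a fixed window after recorded on-demand C1-INH or kallikrein-inhibitor use. Seven days is a workable example because Protocol 5.2, exclusion 4c, uses that interval before Screening for other prophylactic therapies. It is a convention from the protocol, not a measured assay carry-over time.
3. Pre-specify a sensitivity summary that omits flagged post-dose values and replaces a flagged Day 1 baseline with the Screening PD sample, provided that sample passes the same window. This can be checked because medications from 30 days before consent are recorded (Protocol 6.3). Show it beside the as-observed result.
4. State that unscheduled attack-visit samples are not eligible as PD baseline.

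The cost is SAP wording and one derivation from treatment dates and times already collected. In the sensitivity summary there will be fewer values, some baselines will be about 8 weeks old, and the exclusions may be informative, which is why both versions are needed. No change to rescue treatment, dosing or visits is implied.
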